#### 12.1.4 Unanticipated adverse device effects (UADEs)

Unanticipated adverse device effect (UADE) is any serious adverse effect on health or safety or any life-threatening problem or death cause by or associated with, a device, if that effect, problem, or death was not previously identified in nature, severity, or degree of incidence in the investigation plan or application, or any other unanticipated serious problem associated with a device that relates to the rights, safety or welfare of subjects.

#### 12.1.5 Expectedness

Adverse events (AEs) and adverse device effects (ADEs) can be 'Expected' or 'Unexpected'.

##### 12.1.5.1 Expected adverse event or adverse device effect

Expected AEs and ADEs are those that have been previously identified as resulting from administration of the agent or use of the device. For the purposes of this study, an AE or ADE is considered expected when it appears in the current AE/ADE list, the Investigator's Brochure, the Instructions for Use or is included in the informed consent document as a potential risk.

Refer to Section 11.2 and 11.3 for expected adverse events associated with LUM015 and expected adverse device effects associated with the imaging device, respectively.

##### 12.1.5.2 Unexpected adverse event or adverse device effect

For the purposes of this study, an AE or ADE is considered unexpected when it varies in nature, intensity or frequency from information provided in the current AE/ADE list, the Investigator's Brochure, the Instructions for Use, or when it is not included in the informed consent document as a potential risk.

LUMICELL CONFIDENTIAL

This document is confidential. Do not disclose or use except as authorized.

### 12.1.6 Attribution

Attribution is the relationship between an adverse event or serious adverse event and the study treatment. Attribution will be assigned as follows:

- Definite – The AE or ADE is clearly related to the study treatment.
- Probable – The AE or ADE is likely related to the study treatment.
- Possible – The AE or ADE may be related to the study treatment.
- Unlikely - The AE or ADE is doubtfully related to the study treatment.
- Unrelated - The AE or ADE is clearly NOT related to the study treatment.

### 12.2 Procedures for recording and reporting safety

The principal investigator will assess the occurrence of AEs, SAEs, ADEs and UADEs at all subject evaluation time points during the study.

All AEs, SAEs, ADEs and UADEs whether reported by the subject, discovered during questioning, directly observed, or detected by physical examination, laboratory test or other means, will be recorded in the subject's medical record and on the appropriate study-specific case report forms.

For events related to the imaging agent, the descriptions and grading scales found in the revised NCI Common Terminology Criteria for Adverse Events (CTCAE) version 5.0 will be utilized for AE reporting. All appropriate treatment areas should have access to a copy of the CTCAE version 5.0.

A copy of the CTCAE version 5.0 can be downloaded from the CTEP website at:

[https://ctep.cancer.gov/protocolDevelopment/electronic\\_applications/ctc.htm](https://ctep.cancer.gov/protocolDevelopment/electronic_applications/ctc.htm)

### 12.3 Reporting requirements

The study must be conducted in compliance with FDA regulations, local safety reporting requirements, and reporting requirements of the principal investigator and/or IRB.

The Investigator will be responsible to report SAEs that occur at the Institution to the IRB in accordance with IRB requirements. It is the responsibility of the principal investigator to report serious adverse events to Lumicell and/or others as described below.

### 12.4 Reporting to Lumicell

#### 12.4.1 Serious Adverse Event Reporting

All serious adverse events that occur after the initial dose of LUM015 Imaging Agent must be reported to Lumicell using the provided SAE form. This includes events meeting the following criteria:

- Grade 2 (moderate) and Grade 3 (severe) Events – Only events that are unexpected and possibly, probably or definitely related/associated with the intervention (with the exception of an allergic reactions, which will also be included as SAEs).
- All Grade 4 (life-threatening or disabling) Events – Unless expected AND specifically listed in the protocol as not requiring reporting.

LUMICELL CONFIDENTIAL

This document is confidential. Do not disclose or use except as authorized.

- All Grade 5 (fatal) Events – When the subject is enrolled and actively participating in the trial OR when the event occurs within 30 days of the last study intervention.

Note: If the subject is in long term follow up, report the death at the time of continuing review.

The principal investigator must report each serious adverse event to Luminicell within 24 hours of learning of the occurrence. In the event that the Investigator does not become aware of the serious adverse event immediately (e.g., subject sought treatment elsewhere), the principal investigator is to report the event within 24 hours after learning of it and document the time of his or her first awareness of the adverse event. Report serious adverse events by telephone, email or facsimile to:

To Luminicell:  
[name], PhD  
[contact]  
Email: [[contact]](mailto:[contact])  
[contact]

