#### 12.1.2 Serious adverse event (SAE)

A serious adverse event (SAE) is any adverse event, occurring at any dose and regardless of causality that:

- Results in death
- Is life-threatening. Life-threatening means that the person was at immediate risk of death from the reaction as it occurred, i.e., it does not include a reaction which hypothetically might have caused death had it occurred in a more severe form.
- Requires or prolongs inpatient hospitalization (i.e., the event required at least a 24-hour hospitalization or prolonged a hospitalization beyond the expected length of stay). Hospitalization admissions and/or surgical operations scheduled to occur during the study period but planned prior to study entry are not considered SAEs if the illness or disease existed before the person was enrolled in the trial, provided that it did not deteriorate in an unexpected manner during the trial (e.g., surgery performed earlier than planned).
- Results in persistent or significant disability/incapacity. Disability is defined as a substantial disruption of a person's ability to conduct normal life functions.
- Is a congenital anomaly or birth defect; or

LUMICELL CONFIDENTIAL

This document is confidential. Do not disclose or use except as authorized.

- Is an important medical event when, based upon appropriate medical judgment, it may jeopardize the subject and require medical or surgical intervention to prevent one of the outcomes listed above. Examples of such medical events include allergic bronchospasm requiring intensive treatment in an emergency room or at home; blood dyscrasias or convulsions that do not result in inpatient hospitalization, or the development of drug dependency or drug abuse.

Events **not** considered to be serious adverse events are hospitalizations for:

- routine treatment or monitoring of the studied indication, not associated with any deterioration in condition, or for elective procedures
- elective or pre-planned treatment for a pre-existing condition that did not worsen
- respite care

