#### **13.4 Data Safety Monitoring Board**

An independent Data Safety Monitoring Board (DSMB) will be established to review the safety of the LUM Imaging System and to review any SAEs that occur during the study. The DSMB will develop and follow a DSMB Charter. The DSMB will be composed of at least 2 oncology specialists (at least one of whom specializes in surgical oncology) and a statistician. The DSMB will be provided with all reports of adverse events including SAEs regardless of investigator causality assessments.

Following the initial meeting, DSMB meetings will occur on a periodic basis in accordance with the DSMB charter. The chairperson of the DSMB will also be immediately provided with the report of any SAE that is judged as possibly, probably, or definitely attributable to treatment with the investigational product. The charter of the DSMB will specify that this committee is charged with providing periodic reports to Luminicell that contain recommendations that include, but are not limited to, (a) continuation of the study, and (b) termination of the study.

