4.5 Safety analysis

Safety data will be reported as:

- Adverse events stratified by severity and relatedness to drug/device.
- Serious adverse events stratified by severity and relatedness to drug/device.
- Adverse events coded per MedDRA guidelines
- Adverse events by preferred term per MedDRA (sorted by descending occurrences for each preferred term).

Adverse events will be reported by the clinical trial sites and data is recorded in the eCRF. However, a Luminell representative is responsible for assigning the 'expectedness' of any event as described in the study plans or protocols

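### Protocol 12.4.1 requires every SAE on the SAE form but then limits Grade 2–3 events to unexpected, related ones; it needs reconciling with 12.1.2, 12.4.3 and 13.4

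*Protocol*

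**What the plan says.** Protocol 12.1.2 defines seriousness by outcome: "A serious adverse event (SAE) is any adverse event, occurring at any dose and regardless of causality that" leads to one of the listed results, such as death or hospitalization. It sets no condition on CTCAE grade or expectedness.

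Protocol 12.4.1 opens with a general duty: "All serious adverse events that occur after the initial dose of LUM015 Imaging Agent must be reported to Lumicell using the provided SAE form". The next sentence is "This includes events meeting the following criteria", followed by a list by grade:
- Grades 2 and 3: "Only events that are unexpected and possibly, probably or definitely related/associated with the intervention", with a parenthesis "with the exception of an allergic reactions, which will also be included as SAEs".
- Grade 4: all events, "Unless expected AND specifically listed in the protocol as not requiring reporting".
- Grade 5: fatal events during participation or within 30 days of the last study intervention.

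After the list, the section requires each SAE to reach the sponsor within 24 hours of the investigator learning of it.

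Protocol 12.4.3 sends non-serious events to the sponsor on the adverse event CRF. Protocol 13.4 sets up a DSMB to review any SAEs and states: "The DSMB will be provided with all reports of adverse events including SAEs regardless of investigator causality assessments". It also gives the chair immediate notice of any SAE judged at least possibly related, with no condition on expectedness.

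On recording, Protocol 12.2 and 12.8 require all adverse events, serious or not, on the case report forms. SAP 4.5 lists "Serious adverse events stratified by severity and relatedness to drug/device" among its safety outputs and says that site-reported events are recorded in the eCRF.

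**The concern.** The first sentence of 12.4.1 and its Grade 2–3 item give different answers for the same event. The general duty covers every SAE, while the item filters on expectedness and on the investigator's causality judgement. Section 12.1.2 leaves causality out of the definition, and 13.4 says the DSMB's input should not depend on it.

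Prompt, complete reporting of serious events is at stake. LUM015 is given 2 to 6 hours before surgery, so attributing a perioperative event to the agent or to the operation is difficult. Protocol 11 describes limited prior exposure: 15 Phase 1 patients and 55 injected in Phases A and B (15 + 55 = 70), and one anaphylactic reaction among the first 4 Phase C patients. A DSMB recommendation after cumulative safety review is one of the stopping rules in Protocol 8.7. With up to 20 sites, the rule could be applied in more than one way.

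**Working it through.** No arithmetic applies, and the plan gives no figure to reproduce. The check is to take event types that the sections treat differently and follow each through the text.

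| Event | SAE under 12.1.2? | 12.4.1, opening sentence | 12.4.1, Grade 2–3 item | 13.4 |
|---|---|---|---|---|
| A. Grade 3, prolongs hospitalization, judged unrelated | Yes | SAE form | Not admitted | DSMB reviews it |
| B. Grade 3, serious, related, expected, not allergic | Yes | SAE form | Not admitted | DSMB reviews it; chair told at once |
| C. Grade 2, unexpected, related, meets no seriousness criterion | No | Not covered | Admitted | Adverse event report only |
| D. Grade 2–3 allergic reaction, expected, serious | Yes | SAE form | Admitted through the parenthesis | DSMB reviews it; chair told at once if related |

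**Events A and B.** The two parts of 12.4.1 conflict. If a site follows the item, no SAE form is sent. Section 12.4.3 names no other reporting route to the sponsor for these events, since it covers non-serious events only. For B, 13.4 expects immediate notice to the chair of an event that the item would keep off the form.

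**Event C.** The conflict runs the other way. If the list adds to the opening sentence, C goes on the SAE form although it does not meet 12.1.2. The list is offered as what the SAE reporting duty includes, so C would count as an SAE.

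**Event D.** Protocol 11.2 now classes anaphylaxis as expected. The parenthesis keeps it reportable on either reading, so the main known serious risk is not affected.

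**Who judges expectedness.** SAP 4.5 gives this to a sponsor representative, yet the Grade 2–3 item makes it a condition of the site's own 24-hour report. The site would have to decide something that the SAP assigns to someone else.

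**SAE tables.** Sections 12.2 and 12.8 put A and B on a CRF without any filter on grade, expectedness or attribution, and SAP 4.5 points to the eCRF. Neither document says that the tables are built from the SAE form, or where the SAE flag comes from.

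**The case against.** The strongest defence is that 12.4.1 is not restrictive at all. Two unconditional duties surround the list: all SAEs on the form, and each within 24 hours. The linking words are those of inclusion. Grade is not seriousness, so the list can be read as extending the form to some Grade 2–3 events that are not serious by outcome.

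A reader might infer that the allergic-reaction parenthesis rules this out, since it would be superfluous if every SAE were already reportable. That does not follow. On the additive reading, a non-serious allergic reaction is expected and would fall outside the extension, so the parenthesis is needed to bring it in. The parenthesis does not decide between the readings.

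The defence also notes other safeguards. All events go on CRFs, a Medical Safety Monitor reviews adverse event data on an ongoing basis (13.2), monitors verify critical data against source (13.3), and 13.4 gives the DSMB adverse event reports generally. The expected branch looks narrow: Table 3 lists only extravasation (minor), chromaturia (negligible) and anaphylaxis/hypersensitivity, and 11.3 lists no expected device effects. The Investigator's Brochure, Instructions for Use and consent form can add expected events under 12.1.5.1, but they are not available here.

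Much of this stands. 12.4.1 is contradictory, not a clear exclusion, and the most likely affected event is a serious Grade 2–3 event judged unrelated. But *Only* is a word of limitation, and the Grade 4 item is also written as a carve-out, so a site could reasonably read the list as a limit. The additive reading does not restore agreement with 12.1.2 either, because it admits event C.

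**Conclusion.** The contradiction is real and worth correcting. On the restrictive reading, a serious Grade 2–3 event judged unrelated or expected, other than an allergic reaction, could go without the 24-hour SAE form and be missed or delayed in expedited and DSMB review. On the additive reading, some events outside 12.1.2 are counted as SAEs. Either way, the set reported can differ from the set defined.

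The size cannot be estimated: the documents give no rate of serious events by grade, expectedness or attribution. The DSMB consequence assumes that its SAE information, including the chair's notice, depends on the sponsor receiving the form, which the documents do not state.

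A reader might go further and infer that the SAE tables by severity and relatedness would be incomplete. The documents do not support that. Every SAE must be on a CRF, and the SAP refers to the eCRF. Loss would arise only if the SAE flag or dataset were taken from the SAE form, a point on which both documents are silent.

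**What to change.** Reconcile 12.4.1 with 12.1.2, 12.4.3 and 13.4:
- State that every event meeting 12.1.2 goes on the SAE form within 24 hours, whatever its grade, expectedness or attribution.
- Label the grade list as additional events to report, delete *Only*, and say that an event reported solely through the list is not an SAE unless it meets 12.1.2.
- State in the SAP that the SAE tables use the 12.1.2 seriousness flag in the eCRF.

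The cost is wording and a few more SAE forms. Under Protocol 14.1 the protocol change needs IRB approval and submission to the FDA. For patients already treated, a listing of events marked serious in the eCRF that have no SAE form would show whether any were missed.

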#### 12.4.2 Unanticipated adverse device effects

All unanticipated adverse device effects (UADEs) that occur during the study are considered serious and must be reported to Luminicell using the provided SAE form.

The principal investigator must report each unanticipated adverse device effect to Luminicell within 24 hours of learning of the occurrence. In the event that the Investigator does not become aware of the unanticipated adverse device effect immediately (e.g., subject sought treatment elsewhere), the principal investigator is to report the event within 24 hours after learning of it and document the time of his or her first awareness of the adverse device effect. Report unanticipated adverse device effects by telephone, email or facsimile to:

To Luminicell:  
[name], PhD  
[contact]  
Email: [[contact]](mailto:[contact])  
[contact]

#### 12.4.3 Non-serious adverse event and adverse device effect reporting

Non-serious adverse events and non-serious adverse device effects will be reported to Luminicell on the adverse events Case Report Forms.

### 12.5 Reporting to the Institutional Review Board (IRB)

The investigative site will report adverse events, serious adverse events, adverse device effects and unexpected adverse device effects directly to the IRB in accordance with IRB requirements.

### 12.6 Reporting to the Food and Drug Administration (FDA)

Luminicell or its agents will report to the FDA via their IDE as required in 21 CFR Parts 312 & 812 and as additionally described in this protocol.

LUMICELL CONFIDENTIAL

This document is confidential. Do not disclose or use except as authorized.

## 12.7 Reporting to hospital risk management

The principal investigator will report to their local Risk Management office any subject safety reports or sentinel events that require reporting according to institutional policy.

## 12.8 Monitoring of adverse events/adverse device effects and period of observation

All adverse events and adverse device effects, both serious and non-serious, and deaths that are encountered from initiation of study intervention, throughout the study, and within the first post-operative follow-up visit should be followed to their resolution, or until the principal investigator assesses them as stable, or the principal investigator determines the event to be irreversible, or the subject is lost to follow-up. The presence and resolution of AEs, ADEs, SAEs and UADEs (with dates) should be documented on the appropriate case report form and recorded in the subject's medical record to facilitate source data verification.

For some SAEs/UADEs, the investigator or designee may follow-up by telephone, fax, and/or monitoring visit to obtain additional case details deemed necessary to appropriately evaluate the SAE/UADE report (e.g., hospital discharge summary, consultant report, or autopsy report).

Subjects should be instructed to report any serious post-study event(s) that might reasonably be related to participation in this study. The principal investigator should notify Lumicell and the IRB of any unanticipated death or adverse event occurring after a subject has discontinued or terminated study participation that may reasonably be related to the study.

## 12.9 Protocol deviations

Protocol deviations to ongoing studies are any unapproved changes in the study design and/or procedures that are within the Investigator's control and not in accordance with the IRB approved protocol. The Principal Investigator will complete the Protocol Deviation form provided in the Study Binder. Additionally, the reviewing IRB has to be contacted (if applicable per the IRB's requirements) by the Investigator if a Protocol Deviation might either affect the participant's right, safety or well-being, or might significantly affect the completeness, accuracy and reliability of the data. The Protocol Deviation form provided by Lumicell will be used for this purpose.

**Note:** The Principal Investigator will summarize any protocol deviations noted during the course of the study in a final statement.

In the event that the deviation was identified by the Investigator, the Investigator may use the Lumicell deviation form to summarize and assess the impact of the deviation. Similarly, the Lumicell protocol deviation form may be utilized to communicate a deviation that is identified by Lumicell to the investigator. In both cases, the Investigator must provide Lumicell with a copy of the form submitted to their IRB or use the Lumicell form to document the deviation. The deviation will be categorized in the description section of the form as a Protocol Waiver or Protocol Deviation.

Examples of major Protocol Deviations include, but are not limited to the following:

- Inadequate or nonexistent informed consent
- Unreported Adverse Events/Adverse Device Effects

LUMICELL CONFIDENTIAL

This document is confidential. Do not disclose or use except as authorized.

- Data Corruption or falsified data

## 13 DATA AND SAFETY MONITORING

### 13.1 Data reporting

#### 13.1.1 Method

Lumicell will collect, manage, and monitor data for this study.

#### 13.1.2 Data submission

It is the expectation that all case report forms (CRFs) will be completed in a contemporaneous manner at the time of study related procedures. Timely completion of the CRFs will allow Lumicell to monitor the study conduct and data in an effective manner.

### 13.2 Safety review

For this study, an independent safety reviewer (Medical Safety Monitor) will review and monitor adverse events data from this trial on an ongoing basis. The Medical Safety Monitor will be a clinical specialist with experience in oncology and who has no direct relationship with the study. Information that raises any questions about subject safety will be addressed with the Principal Investigator and study team.

### 13.3 Monitoring

Lumicell's monitoring process will be initiated with the initial visits to sites to assure that they meet the qualification requirements and have adequate resources and experience to conduct the study protocol. When the site has met all qualification criteria, submitted all initial regulatory documentation, and received IRB approval for the study, Lumicell will conduct a study initiation visit (either face to face, or via web) in which the site team will receive protocol specific training in addition to a review of all investigator responsibilities, and expectations of Lumicell. Throughout the conduct of the study Lumicell will conduct intermittent site visits to assure compliance with the protocol and all applicable regulations. During these visits, there will be a source data verification of critical data points transcribed to the CRF. At study completion, Lumicell will conduct a study closure visit. This study visit will assure that all site regulatory documentation is present and updated; all data queries are resolved; investigator sign-off/approval of all applicable study data submitted to Lumicell has occurred; and all final disposition instructions from Lumicell have been delivered to the site investigator.

Involvement in this study as a participating investigator implies acceptance of the approved protocol, the potential for audits or inspections, including source data verification, by representatives of the FDA, Lumicell (or their affiliates), the institutional review board, or their representatives. The purpose of these audits or inspections is to examine study-related activities and documents to determine whether these activities were conducted and data were recorded, analyzed, and accurately reported in accordance with the protocol, institutional policy, Good Clinical Practices (GCPs), and any applicable regulatory requirements.

LUMICELL CONFIDENTIAL

This document is confidential. Do not disclose or use except as authorized.

All data will be monitored for timeliness of submission, completeness, accuracy, and adherence to protocol requirements. Monitoring will begin at the time of subject registration and will continue during protocol performance and completion.

